10.2 Demographics and Subject Characteristics at Baseline

Subject demographics, medical history, concomitant medications will be tabulated and summarized descriptively.

10.3 Statistical Analysis Methods

This is an exploratory study to evaluate safety and efficacy of the investigational enlighten device, therefore, formal statistical analyses are not planned.

Outcome measures will be assessed around multiple endpoints. These measures will be: degree of improvement as assessed by the Investigator, [REDACTED] and safety. Additional assessments may also be performed but are not considered part of the analysis (i.e. subject post-treatment questionnaire). The specific assessment tools, collection method and time points are listed herein.

10.3.1 Analysis Sets

The efficacy analysis set will include all subjects who received at least one laser treatment session and complete at least one follow-up visit. The safety analysis set will include all subjects enrolled in the study who had at least one laser treatment session.

Missing data will not be imputed for efficacy or safety endpoints.

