4.3 Study Effectiveness Assessments

4.3.1 Investigator Assessments

4.3.1.1 *Investigator's Global Assessment of Improvement*

At 12 weeks post-final treatment, the Investigator will be asked to rate the degree of improvement in the appearance of the subject's treated area from baseline using the Physician's Global Assessment Scale:

4 = Very Significant or Complete Clearing ([REDACTED])

3 = Significant Clearing ([REDACTED])

2 = Moderate Clearing ([REDACTED])

1 = Mild Clearing ([REDACTED])

0 = No Clearing ([REDACTED])

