7.2 Recording ADEs and SADEs

All ADEs/SADEs will be: (1) evaluated and must be recorded in the subject's medical chart and in the study case report forms (CRFs); (2) monitored and tracked from the time of the first treatment with the Cutera Enlighten laser system.

At each contact with the subject, the investigator must seek information on ADEs/SADEs by specific questioning and, as appropriate, by examination. ADEs/SADEs may be observed by the investigator and/or clinical research staff, elicited from the subject and/or family member or volunteered by the subject. All observed and volunteered adverse signs and symptoms, anticipated or unanticipated, regardless of severity or frequency, will be recorded in the case histories (medical chart and CRFs). Included in the description should be the nature of the sign or symptom, the date of onset, date of resolution (duration), the severity, anticipated or unanticipated, the relationship to study treatment or other therapy, the action taken (if any), and the outcome.

All SADEs, anticipated or unanticipated, must be reported to Cutera immediately but not later than 5 working days. The SADE must be recorded in: (1) the AE CRF and (2) a written report must be submitted to Cutera within five (5) working days after the investigator first learns of the event and is to include a full description of the event and sequelae, in the format detailed by the Cutera Serious Adverse Device Effect Form.

7.3 Follow-up of Subjects after ADEs and SADEs:

All reported ADEs/SADEs should be followed until resolution or until the subject's participation in the study ends. Resolutions of ADEs/SADEs are to be documented on the appropriate CRFs. All ADEs that result in permanent discontinuation from this clinical trial, whether serious or not, should also be reported on the subject Non-Completion of Study Form.

8 Potential Risks / Benefits

8.1

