10 DATA ANALYSIS PLAN

10.1 Sample Size

Up to 20 subjects will be enrolled in this exploratory study.

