10.3.1.1 Efficacy Analyses

Descriptive statistics such as mean, standard deviation, median and range will be performed for:

- The degree of improvement at 12 weeks post-final treatment as assessed by the Investigator, using the Physician's Global Assessment tool.
- [REDACTED]
[REDACTED]

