10.3.1.2 Safety Analyses

The safety variables for this study are:

- Incidence and severity of adverse effects during study duration (to be displayed descriptively as counts and frequency distributions)
- Subject discomfort (pain) during treatment (to be descriptively displayed).

Enrolled subjects who received at least one treatment will be included in the safety analyses. Device-related and procedure-related adverse effects (AEs) and subjects who prematurely terminate from the study due to an adverse device effect, including the treatment-related pain ratings, as reported on case report forms will be tabulated and analyzed. For a given AE term, counting will be done by subject, not by event, i.e. for a subject reporting the same AE more than once, the event will be counted only once, at the most severe and most-related occurrence. The number and percentage of subjects experiencing each AE Term will be descriptively summarized. Statistical hypothesis testing will not be performed for safety data.

Interim analyses of adverse events and adverse device effect incidence and severity will be performed when all treated subjects have completed the 12 week post-final treatment visit. At the conclusion of the study, complete analyses of the safety variables will be displayed descriptively.

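### Does summarising the 12-week Investigator score without imputation, and without a stated requirement to show the numbers behind it, call for a change to the plan?

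*Combined protocol and SAP*

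**What the plan says.** Section 10.3.1 of the combined protocol and SAP defines two sets. The efficacy set is "all subjects who received at least one laser treatment session and complete at least one follow-up visit". For safety, "The safety analysis set will include all subjects enrolled in the study who had at least one laser treatment session". The same section adds: "Missing data will not be imputed for efficacy or safety endpoints".

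The readable efficacy endpoint is a single rating. Section 4.3.1.1 states: "At 12 weeks post-final treatment, the Investigator will be asked to rate the degree of improvement", on a scale from 0 (no clearing) to 4 (very significant or complete clearing). Section 10.3.1.1 introduces its summary with "Descriptive statistics such as mean, standard deviation, median and range will be performed for" and then names this rating. The item after it is redacted.

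On size and purpose, section 10.1 says "Up to 20 subjects will be enrolled in this exploratory study", and section 10.3 plans no formal statistical analysis.

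Several sections deal with subjects who leave:
- Section 10.3.1.2 tabulates "subjects who prematurely terminate from the study due to an adverse device effect".
- Section 7.3 says that adverse device effects leading to permanent discontinuation "should also be reported on the subject Non-Completion of Study Form".
- Section 12.3.2 treats a visit missed within its window as a protocol deviation.
- Section 5.3 requires three documented contact attempts before a subject counts as lost, and has the investigator try to obtain a last clinical assessment at withdrawal.

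**The concern.** The efficacy set does not require the 12-week visit, yet the endpoint exists only at that visit. With no imputation, a subject in the set who lacks a 12-week rating appears to add nothing to the mean, standard deviation, median or range. A treated subject with no follow-up visit is outside the set altogether. The summary could thus rest on fewer subjects than the efficacy set, which could itself be smaller than the number treated. The named statistics do not include n or the number missing.

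There is no comparator, so the observed figure is read on its own. If subjects with poor results were the ones not rated, the reported improvement would be too high. If subjects with good results were missing, it would be too low. If loss were unrelated to outcome, there would be no bias. Participation lasts about 5 to 16 months (section 4.2), so some missing ratings are plausible. A reader not given the three numbers could not judge how much of the treated group the summary covers.

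**Working it through.** The plan has no figure to reproduce. It states no power, significance level, effect size or dropout rate, and 20 is a cap without a calculation. The check is a bound on what missing ratings could do, followed by a reading of what the plan already makes visible.

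**Inputs from the documents.** Scale 0 to 4 (section 4.3.1.1); at most N = 20 subjects (section 10.1); no imputation (section 10.3.1).

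**Inputs assumed for illustration.** All 20 are treated, d of them have no 12-week score, and the mean among those scored is m = 2.5.

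**Formula.** With u the unknown mean of the unscored subjects, the all-treated mean is (m(N − d) + u·d)/N. It is lowest at u = 0 and highest at u = 4, so the width of the range is 4d/N, whatever m is. For N = 20 that is 4/20 = 0.20 points per unscored subject. With fewer treated it is larger: for N = 10 it is 4/10 = 0.40.

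| d (assumed) | Scored | Lowest (u = 0) | Highest (u = 4) | Width 4d/20 |
|---|---|---|---|---|
| 2 | 18 | 18 × 2.5/20 = 2.25 | (45 + 8)/20 = 2.65 | 0.40 |
| 4 | 16 | 16 × 2.5/20 = 2.00 | (40 + 16)/20 = 2.80 | 0.80 |
| 6 | 14 | 14 × 2.5/20 = 1.75 | (35 + 24)/20 = 2.95 | 1.20 |

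These are extreme bounds. If the unscored would have scored the same on average as the scored (u = 2.5), the all-treated mean is 2.50 for every d.

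The choice of denominator matters in the same way. Suppose 20 treated, 18 in the efficacy set, 16 scored, and 8 of those rated 3 or 4. Then 8/16 = 50%, 8/18 = 44% and 8/20 = 40%. The readable plan sets no such cut-off and does not call for this percentage.

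**What the plan already makes visible.**
- *Number treated.* Section 10.3.1.2 requires the number and percentage of subjects with each adverse effect term, among those who had at least one treatment. Those percentages cannot be formed without the number treated.
- *Number scored.* The wording of section 10.3.1.1 gives examples, not a closed list. A mean and standard deviation are routinely tabulated with their n.
- *Number in the efficacy set.* The set is defined in section 10.3.1, so its size is a simple count.
- *Reasons for leaving.* The sources in sections 5.3, 7.3, 10.3.1.2 and 12.3.2 record part of this. The readable text does not link them to missing 12-week scores.

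**How a score comes to be missing.** Section 4 leaves the number of treatments to the Investigator, and the rating is timed from the last treatment given. Stopping treatment early therefore need not cost a rating; leaving the study does. Section 5.3 asks that subjects stay through follow-up where possible. Section 10.3.1.2 times its interim safety analysis to when all treated subjects have had the 12-week visit, so the plan expects near-complete attendance, though it cannot guarantee it.

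**The case for a change.** The strongest case for a change is that it would be cheap and would settle matters before the data are seen. The plan is more explicit about safety, where it asks for counts, frequency distributions and percentages, than about the five-category efficacy rating. The only discontinuation count required in the readable analysis text is for adverse device effects. A routine n beside the mean would not necessarily bring all three numbers or the reasons for missing ratings. Nor does the plan say whether a last assessment obtained at withdrawal enters the 12-week summary. That the summary uses only subjects with a 12-week score is therefore an inference, though a strong one given the no-imputation rule and the single time point.

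What stands is that the text is silent on these details, and that a careful report would give the number scored beside the other two and say how withdrawal assessments were handled. What does not stand is that the silence is a flaw in the analysis. Following the plan as written gives a sound descriptive summary of the ratings obtained. Wider remedies, such as category percentages over the safety set or a summary counting unscored subjects as 0, are preferences in presentation that go beyond the gap. The first would also replace the plan's own efficacy set as denominator. Finally, text next to the efficacy summary and much of sections 6 and 12 cannot be read, so the plan itself cannot be shown to lack the requirement.

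**Conclusion.** No change to the plan follows. The three numbers can differ, and the readable text does not require them side by side, but this is a missing reporting detail that analysts fill in as a matter of course. Not imputing is acceptable in a descriptive, single-arm study of at most 20 subjects in which no readable test or success criterion depends on the mean.

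The possible size is 0.20 points on the 0 to 4 scale per unscored subject when 20 are treated, for example a width of 0.80 with 4 unscored. That is a worst-case range, not an estimate of bias. The numbers unscored and the mean of 2.5 are assumptions, and the documents do not show the direction or size of any bias. The conclusion rests on the readable text and covers the Investigator's 12-week assessment only, since the other efficacy measures are redacted. It also relies on the ordinary practice of reporting n with a mean.

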10.3.1.1 Efficacy Analyses

Descriptive statistics such as mean, standard deviation, median and range will be performed for:

- The degree of improvement at 12 weeks post-final treatment as assessed by the Investigator, using the Physician's Global Assessment tool.
- [REDACTED]
[REDACTED]

10.3.1.2 Safety Analyses

The safety variables for this study are:

- Incidence and severity of adverse effects during study duration (to be displayed descriptively as counts and frequency distributions)
- Subject discomfort (pain) during treatment (to be descriptively displayed).

Enrolled subjects who received at least one treatment will be included in the safety analyses. Device-related and procedure-related adverse effects (AEs) and subjects who prematurely terminate from the study due to an adverse device effect, including the treatment-related pain ratings, as reported on case report forms will be tabulated and analyzed. For a given AE term, counting will be done by subject, not by event, i.e. for a subject reporting the same AE more than once, the event will be counted only once, at the most severe and most-related occurrence. The number and percentage of subjects experiencing each AE Term will be descriptively summarized. Statistical hypothesis testing will not be performed for safety data.

Interim analyses of adverse events and adverse device effect incidence and severity will be performed when all treated subjects have completed the 12 week post-final treatment visit. At the conclusion of the study, complete analyses of the safety variables will be displayed descriptively.

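### The final safety tabulation is defined only for device- and procedure-related effects, its scope is worded inconsistently, and no all-cause table is specified although all adverse signs and symptoms are recorded

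*Combined protocol and SAP*

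**What the plan says.** Section 10.3.1.2 (Safety Analyses) first lists a safety variable without any relatedness qualifier: "Incidence and severity of adverse effects during study duration (to be displayed descriptively as counts and frequency distributions". The sentence that then says what will be tabulated is narrower: "Device-related and procedure-related adverse effects (AEs) and subjects who prematurely terminate from the study due to an adverse device effect", with treatment pain ratings included. The counting rule works per subject and per term: "the event will be counted only once, at the most severe and most-related occurrence". The output is described as "The number and percentage of subjects experiencing each AE Term will be descriptively summarized". The section also plans an earlier look, and here it names two kinds of event: "Interim analyses of adverse events and adverse device effect incidence and severity will be performed". That look takes place once all treated subjects have reached the 12-week visit after the last treatment. At study end, the safety variables are to be displayed completely and descriptively.

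Section 7.2 (Recording ADEs and SADEs) sets a wide recording rule: "All observed and volunteered adverse signs and symptoms, anticipated or unanticipated, regardless of severity or frequency, will be recorded in the case histories". Each record is to include, among other items, "the relationship to study treatment or other therapy".

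The safety endpoints in 4.1.1.1 are stated in terms of adverse device effects. Section 4 describes a single-center, open-label, uncontrolled study in up to 20 subjects.

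**The concern.** Relationship to treatment is an attribute recorded for each event. The defining sentence in 10.3.1.2 uses it as a condition for entering the table. With no comparator, the background rate of skin complaints cannot be observed, so relatedness can only be judged case by case, by people who know that the subject was treated. A reader of the results would then see incidence after attribution, with no means of seeing incidence before it.

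Early terminations raise the same issue. Section 5.3 gives several routes out of the study, including the subject's own choice, noncompliance, the investigator's view of the subject's interest, and a serious reaction. Only terminations ascribed to a device effect are named for tabulation. A subject who leaves for discomfort that is recorded as personal choice would not appear.

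Safety of an investigational version of the device is a study objective (section 3), and an exploratory study is where unexpected effects should be visible.

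**Working it through.** **1. Which scope does 10.3.1.2 set?** The terms, side by side:

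| Place | Term used | Relatedness qualifier |
|---|---|---|
| 4.1.1.1, endpoints | adverse device effects | yes, by name |
| 4.4.1, heading | adverse events | no |
| 4.4.1, text | adverse device effects | yes, by name |
| 4.4.3, phone follow-up | adverse events | no |
| 10.3.1.2, listed variable | adverse effects | no |
| 10.3.1.2, tabulation sentence | device- and procedure-related adverse effects, abbreviated AEs | yes |
| 10.3.1.2, per-term summary | AE term | inherited from the abbreviation, or none |
| 10.3.1.2, interim | adverse events and adverse device effects | both kinds named |

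The abbreviation can be read in two ways. If AE stands for the whole qualified phrase, the per-term table holds related effects only. If it stands for adverse effects alone, the per-term table could be wider, but the sentence that lists what is tabulated still carries the qualifier. On neither reading does the text state that unrelated events are shown.

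**2. Does the counting rule settle it?** It keeps the most-related occurrence, so relatedness is graded. A grade is just as useful within related events as across all events, so the rule fits either scope.

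**3. Is the recording wider than the tabulation?** Section 7.2 sits under a device-effect heading, but it covers all observed and volunteered signs and symptoms and asks whether each relates to study treatment or to other therapy. That question has a purpose only if events not due to the device are also recorded. The gap is therefore in the analysis plan and not in data capture.

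**4. Size.** The plan gives no attribution rate, alpha, power or effect size, so there is no figure of its own to reproduce. The arithmetic below is for scale only. Inputs: n = 20 is the cap in 10.1; n = 15 and n = 10 are assumptions for smaller enrolment; all event counts are assumptions.

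- Change in a term's incidence per subject whose only event for that term is judged unrelated: 100/n percentage points. For n = 20 this is 5.0, for n = 15 it is 6.7, and for n = 10 it is 10.0.
- Example at n = 20, with exact (Clopper-Pearson) 95% limits, lower = Beta quantile(0.025; x, n − x + 1) and upper = Beta quantile(0.975; x + 1, n − x). Four subjects with a term: 4/20 = 20% (5.7% to 43.7%). If two of them are judged unrelated: 2/20 = 10% (1.2% to 31.7%). The intervals overlap widely, but the reported point estimate is halved.
- No event tabulated at n = 20: the one-sided 95% upper bound is 1 − 0.05^(1/20) = 13.9%, and the upper limit of the two-sided 95% interval is 1 − 0.025^(1/20) = 16.8%. Under the narrow scope, either limit applies to attributed events only.

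**The case against.** The strongest reply is that the section never says that unrelated events are excluded. Its listed variable is unqualified, its interim sentence names adverse events as well as device effects, and its closing sentence promises complete analyses of the safety variables, which could be read as at least as wide as the interim look. That reading is possible, and it is why the point is one of inconsistent scope and not of a firm exclusion. It is not stated, however, and no final all-cause table or table of all terminations by reason is specified.

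Second, the endpoint is adverse device effects, so a table of related effects is legitimate. This stands, and the fix keeps that table.

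Third, the definitions under 7.1 are not visible in the public copy. They may set relatedness categories and say who assigns them. A reader might infer that one unmasked investigator alone decides what is reported. Section 7.2 has the investigator elicit events and the visible text names no independent assessor, but sole attribution remains an inference.

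Fourth, a reader might infer that the effect is always to make the device look safer. Leaving unrelated events out does lower all-cause incidence, but against the stated endpoint misattribution can go either way, because a background complaint can also be called device-related.

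Finally, the study is small and descriptive, with no hypothesis test (10.3, 10.3.1.2). No error rate or sample size is affected.

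**Conclusion.** The point holds in a limited form. The one sentence that defines the safety tabulation is restricted to related effects and device-attributed terminations, other wording in the same section points wider, and the final analysis has no specified all-cause table. Whether the interim and final tables differ in scope cannot be determined from the text, and that is itself part of the problem.

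The documents do not support saying that the plan removes unrelated events from the results, or that they are lost: they are recorded under 7.2 and could be tabulated.

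The size is 5 percentage points of a term's incidence for each affected subject at the cap of 20, and more if fewer are treated. This rests on the narrow reading being applied and on that subject having no related occurrence of the same term. The number of such subjects is unknown, so no overall bias can be stated. The change is worth making because it is cheap and because readers of an uncontrolled study need to see incidence both before and after attribution.

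**What to change.** In 10.3.1.2:

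1. Tabulate all adverse events recorded under 7.2 by term and severity, regardless of relationship, with the existing once-per-subject counting rule.
2. Keep device- and procedure-related effects as a subset table, since they are the endpoint in 4.1.1.1.
3. Tabulate all premature terminations by reason, with those due to an adverse device effect shown as one category.
4. Choose one defined term for all events and one for related effects, use them throughout (including 4.4.1 and 4.4.3), and state that the interim and final tables have the same scope.

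The cost is one or two added descriptive tables and a wording change. The event data are already collected under 7.2. For terminations, check that the non-completion form mentioned in 7.3 records the reason for every early exit, because the visible text describes its use only for device effects.

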Objective	
1. To evaluate the safety of an investigational version of the enlighten™ 532nm /1064nm/670nm laser for photo-rejuvenation.2. To evaluate the efficacy of an investigational version of the enlighten™ 532nm /1064nm/670nm laser for photo-rejuvenation.
Study Design	A single-center prospective, open-label uncontrolled exploratory study. Subjects will receive [REDACTED] laser treatments, [REDACTED] [REDACTED] and will be followed at 2 [REDACTED] [REDACTED] 12 weeks [REDACTED] post-final treatment. In addition, after each treatment, subjects will complete a 3 day post treatment phone follow-up. [REDACTED] [REDACTED]
Enrollment	A maximum of 20 subjects
Study Endpoints	
• Incidence and severity of adverse device effects at 2 weeks post-first treatment.• Incidence and severity of adverse device effects during the study period, including subject pain level during laser treatment.• Degree of improvement in the treated area at 12 weeks post-final treatment as assessed by the Investigator (Physician's Global Assessment of Improvement). [REDACTED]
Subject Population	Female or male subjects, age 18 to 75 years, Fitzpatrick skin types I-VI
Planned Schedule	First subject enrolled: September 2016 Last subject last visit: August 2018

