Nanosecond QS lasers have been widely used for more than 20 years as a safe and effective treatment for skin rejuvenation [18-24]. Laser wavelengths and pulse durations currently available for nanosecond QS laser treatment of pigmented lesions include 532 nm Nd:YAG, 1064 nm Nd:YAG, 755 nm Alexandrite and 694 nm Ruby with pulse durations from 5 to 10 ns (Nd:YAG), 50 to 70 ns (Alexandrite) 25 to 30 ns (Ruby). These wavelengths in the visible and infrared ranges are appropriate for the absorption spectrum of melanin. Melanin, the target pigment for these lasers, is largely present in basal keratinocytes in benign pigmented lesions. During laser procedures, the melanosomes, the organelle which hold the melanin in melanocytes, are rapidly heated [25, 26]. This rapid heating and evaporation of the melanosomes in the skin result in vacuolization.

The current proposed exploratory clinical study described herein intends to evaluate the safety and effectiveness of the investigational laser and the optimal range of treatment parameters for use in skin rejuvenation.

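### Adverse effects are planned only as pooled percentages over Fitzpatrick types I-VI, so an effect confined to a few darker-skinned subjects could not be seen in the safety table

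*Combined protocol and SAP*

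**What the plan says.** The Subject Population entry of the Protocol Summary reads "Female or male subjects, age 18 to 75 years, Fitzpatrick skin types I-VI", and sections 5.1 and 5.1.1 (inclusion criterion 2) repeat the range. On size, section 10.1 says only "Up to 20 subjects will be enrolled in this exploratory study". No quota or minimum per skin type appears in the visible text.

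Section 10.3.1 fixes the denominator: "The safety analysis set will include all subjects enrolled in the study who had at least one laser treatment session". Section 10.3.1.2 then gives incidence and severity "to be displayed descriptively as counts and frequency distributions" and adds: "The number and percentage of subjects experiencing each AE Term will be descriptively summarized". No visible section splits or lists adverse effects by skin type. The baseline plan in section 10.2 is "Subject demographics, medical history, concomitant medications will be tabulated and summarized descriptively"; it does not name skin type.

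The background in section 2.1, describing existing nanosecond Q-switched lasers, states: "Melanin, the target pigment for these lasers, is largely present in basal keratinocytes in benign pigmented lesions". The wavelengths listed there include 532 and 1064 nm. Section 1 gives the study device a wavelength between 660 and 690 nm, plus 532 or 1064 nm.

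**The concern.** Safety is the first objective in the Protocol Summary, and every skin type may enter. If light is absorbed by melanin, the amount of melanin in a subject's skin is a natural candidate for modifying pigment-related adverse effects. A pooled percentage then depends on which skin types happened to enrol as well as on the device.

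At stake is what the safety table can reveal. Suppose most of the 20 subjects are light-skinned and a few darker-skinned subjects have pigment change. The planned table would show a modest overall percentage and give no sign that the events fell in one group. It would look the same if no subject of type V or VI had been treated. The variable needed to tell these situations apart must already be determined for each subject, because it is an inclusion criterion.

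**Working it through.** The plan has no figure to reproduce: 20 is a cap, with no event rate, precision target or power behind it. The check therefore asks what pooling does to an effect confined to one group.

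**Inputs from the protocol.** N = 20 at most (10.1); all six types eligible (5.1.1); one percentage per term over all treated subjects (10.3.1 and 10.3.1.2).

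**Assumptions, not in the documents.** The number of darker-skinned subjects (n_dark), their risk (p_dark) and the risk in the rest (p_light).

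**Dilution.** Expected pooled rate = [n_dark × p_dark + (20 − n_dark) × p_light] / 20. With p_light = 0 this is p_dark × n_dark/20. The chance that no darker-skinned subject has the event is (1 − p_dark)^n_dark.

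| n_dark | Pooled rate at p_dark = 20 / 30 / 50% (p_light = 0) | Chance of no event in n_dark |
|---|---|---|
| 2 | 2 / 3 / 5% | 64 / 49 / 25% |
| 4 | 4 / 6 / 10% | 41 / 24 / 6% |
| 6 | 6 / 9 / 15% | 26 / 12 / 2% |
| 10 | 10 / 15 / 25% | 11 / 3 / 0.1% |

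With p_light = 5% and n_dark = 4, the pooled rates are 8, 10 and 14%. For example, (4 × 0.50 + 16 × 0.05)/20 = 2.8/20 = 14%.

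**What the split would show.** Take n_dark = 4 and two events, both in that group. Exact (Clopper-Pearson) 95% intervals:

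- planned table: 2/20 = 10% (1.2% to 31.7%);
- split table: 2/4 = 50% (6.8% to 93.2%), beside 0/16.

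The events are the same, but only the second display shows where they fell.

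**What the split would not do.** With no events, the exact two-sided upper 95% limit is 1 − 0.025^(1/n):

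| n | Upper limit for 0/n |
|---|---|
| 20 | 16.8% |
| 10 | 30.8% |
| 5 | 52.2% |
| 4 | 60.2% |
| 3 | 70.8% |
| 2 | 84.2% |

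An even spread of 20 over six types is about 3 per type, where zero events still leaves an upper limit of 70.8%. These limits come from the small numbers and would be the same however the table is laid out.

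**The case against.** The strongest reply is that this is an exploratory, uncontrolled study of at most 20 subjects. It plans no formal analysis (10.3) and no hypothesis tests on safety (10.3.1.2). Types I-VI are an eligibility range. A reader might infer that the plan draws a safety conclusion for all six types and that this conclusion is unsupported. The visible text sets no such conclusion or success criterion, so that reading fails. What remains is a limit on what may be said later.

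A reader might also infer that the protocol itself calls melanin the target of the study laser. It does not. The sentence in section 2.1 is about existing nanosecond devices, the device section is blacked out, and the table of contents refers to a picosecond device. The aims also include scars, fine lines, redness and texture. The shared 532 and 1064 nm wavelengths make the inference reasonable, but it remains an inference.

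Nor does the visible text say that pigment change is more frequent in darker skin. Section 2.1 mentions it only for ablative procedures, and the study's risk section is blacked out. Exclusion criteria 16 and 20 keep out subjects prone to pigment change and those who are heavily tanned, which may lower the risk. They do not make the six types alike.

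Two further points stand in part. Section 10.2 is worded generally, so skin type might be tabulated without being named. Section 7.2 requires adverse effects to be recorded for each subject, so the raw data would allow a listing; but the visible plan does not ask for one showing skin type. Hidden sections, including all of section 6, might contain quotas or skin-type provisions, so the point is confined to the visible analysis plan.

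**Conclusion.** The point holds as a gap in planned reporting. In the visible plan adverse effects appear only pooled over all treated subjects, so an effect confined to darker-skinned subjects shrinks by n_dark/20 and its concentration cannot be seen. The factor is arithmetic. Its application here rests on the assumption that skin pigment modifies risk, which is plausible from section 2.1 but not stated.

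No fixed degree of understatement can be claimed. Taking 2% risk in types I-III and 25% in IV-VI, with 2 to 6 such subjects, gives a pooled 4.3% to 8.9%: (18 × 0.02 + 2 × 0.25)/20 = 4.3% and (14 × 0.02 + 6 × 0.25)/20 = 8.9%. A reader might infer a 3- to 6-fold understatement, but that ratio follows from the chosen rates. If the risks were equal, there would be none.

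Pooling is also not the reason the trial cannot establish safety in types V-VI. The small number of subjects is, and the split does not change that.

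**What to change.** - **Section 10.2:** report the number of treated subjects by Fitzpatrick type.
- **Section 10.3.1.2:** keep the pooled figure. Beside it, show each adverse-effect term, pigment change in particular, as n/N by skin-type group with exact 95% intervals. Name the groups in advance, for example I-III and IV-VI.
- **Listing:** give adverse effects by subject with the individual Fitzpatrick type, because a IV-VI group would otherwise hide V-VI behind IV.
- **Interpretation:** limit descriptive safety statements to the types actually treated, with their numbers.

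The cost is one more split and one listing, using a variable already needed for eligibility. No subjects, visits or hypothesis tests are added, so the plan stays descriptive. The downside is small cells with wide intervals. The text should say that the split is there to reveal clustering and does not show safety by type.
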